5.3 Subject Enrollment

Before subjects begin participation in any study-specific activities/procedures, Amgen requires a copy of the site's written Institutional Review Board/Independent Ethics Committee (IRB/IEC) approval of the protocol, informed consent form (ICF), and all other subject information and/or recruitment material, if applicable (see [Section 11.3](#)).

The subject or the subject's legally authorized representative must personally sign and date the IRB/IEC and Amgen approved informed consent before commencement of study-specific procedures.

A subject is considered enrolled when the investigator decides that the subject has met all eligibility criteria. The investigator is to document this decision and date, in the subject's medical record and in/on the enrollment case report form (CRF).

Each subject who enters into the screening period for the study (up to 14 days prior to study day 1) receives a unique subject identification number before any study-related activities/procedures are performed. The subject identification number will be assigned manually. This number will be used to identify the subject throughout the clinical study and must be used on all study documentation related to that subject.

The subject identification number must remain constant throughout the entire clinical study; it must not be changed after initial assignment, including if a subject is rescreened.

5.4 Screen Failures

Screen failures are defined as subjects who consent to participate in the clinical study but are not subsequently enrolled in the study. A minimal set of screen failure information will be collected that includes demography, screen failure details, eligibility criteria, medical history, prior therapies, and any serious adverse events.

Individuals who do not meet the criteria for participation in this study within the 14-day screening period (screen failure) may be rescreened up to 3 times at the discretion of the investigator. Refer to [Section 8.1.1](#) for rescreening procedures.

5.5 Washout Period/Run-in Period/Invasive Procedure(s)

Not applicable

6. Treatments

Study treatment is defined as any investigational product(s), non-investigational product(s), placebo, or medical device(s) intended to be administered to a study subject according to the study protocol.

Note that in several countries, investigational product and non-investigational product are referred to as investigational medicinal product and non-investigational medicinal product, respectively.

The Investigational Product Instruction Manual (IPIM), a document external to this protocol, contains detailed information regarding the storage, preparation, destruction, and administration of each treatment (shown in [Table 6-1](#)).

6.1 Treatment(s) Administered

6.1.1 Investigational Products

Table 6-1. Study Treatments

Study Treatment Name	Amgen Investigational Product: ^a AMG 330	Non-Amgen Investigational Product: ^b Pembrolizumab
Dosage Formulation	Powder for solution for infusion in a vial containing [REDACTED] mg of AMG 330 AMG 330 is formulated with potassium phosphate, captisol, sucrose, polysorbate 80, pH [REDACTED]. IVSS is supplied as a sterile solution in a 10-cc glass vial containing 10 mL deliverable product. The IVSS does not contain an active pharmaceutical ingredient and is a buffered, preservative-free solution ([REDACTED], pH [REDACTED]). The IVSS is intended for pre-treatment of IV bags prior to dilution of AMG 330 drug product.	Solution for infusion
Unit Dose Strength(s)/ Dosage Level(s) and Dosage Frequency	Various dosage level(s) (see Table 4-1 , Table 4-2 , and Table 4-3).	100 mg/4 mL (25 mg/mL) single-dose vials Dosage level(s) 200 mg Q3W
Route of Administration	Continuous IV infusion	Intermittent IV infusion
Accountability	The amount dispensed, date dispensed, and lot number of investigational product is to be recorded on each subject's CRF.	The amount dispensed, date dispensed, and lot number of investigational product is to be recorded on each subject's CRF.
Dosing Instructions	Each vial will be reconstituted with 1.2 mL of sterile water for injection for a final concentration of 0.5 mg/mL AMG 330. The dose, start date/time, stop date/time, lot number of investigational product is to be recorded on each subject's CRF.	The dose, start date/time, stop date/time, lot number of investigational product is to be recorded on each subject's CRF.

CRF = case report form; IV = intravenous; Q3W = every 3 weeks (21 days)

^a AMG 330 will be manufactured and packaged by Amgen and distributed using Amgen clinical study drug distribution procedures.^b Pembrolizumab will be manufactured and packaged by Merck & Co Inc and distributed using Amgen clinical study drug distribution procedures.

6.1.1.1 AMG 330 Dosage, Administration, and Schedule

AMG 330 is administered as a cIV infusion. The infusion bags will be changed by site nursing personnel trained on the protocol and on the proper administration of AMG 330.

The first cycle of AMG 330 treatment is 56-77 days in duration. Please refer to the study schema ([Figure 1-1](#)). The first cycle is followed by a 7-day AMG 330 treatment-free interval. The dosing and schedule will be as outlined in [Table 4-1](#) and [Table 4-2](#).

The drug administration should not be interrupted, if possible. In case of infusion interruption, due to any technical or logistic reason, the interruption should be as short as possible and the infusion continued at the earliest time possible. Every interruption longer than 1 hour should be documented. Administration of dexamethasone premedication will occur as described in [Section 6.7](#).

The start time of infusion should be chosen carefully so as to avoid any interference or inconvenience with time points of safety assessments, PK/pharmacodynamic measurements and changes of infusion bags. The site should record any unscheduled interruption of an infusion on the eCRF, and provide the start and stop date/time of the infusion and the bag change.

AMG 330 should be administered through a central venous access at a constant flow rate. The drug should not be administered as a bolus and flushing residual drug at the time of bag change is prohibited. In the event that administration through a central venous access is not possible, AMG 330 may be administered temporarily through a peripheral venous line if the subject is hospitalized. The final solution for infusion should be administered through a sterile 0.2 µm in-line filter.

Infusion bags should be changed in accordance with local pharmacy standards for infusion of compounded sterile products but at least every 4 days. In the US, infusion bags should be changed at least every other day and in no case should AMG 330 be administered for more than 48 hours at ambient temperature.

The dose, start and stop date/time, and lot number of protocol-specified therapy is to be recorded on each subject's CRF. The date and time of infusion bag changes, all infusion start and stop times, and any dose modifications should also be recorded accurately.

Approved

6.1.1.1.1 Infusion-Free Interval for AMG 330

The planned length of an AMG 330 infusion-free interval between cycles is 1 week (+3 days if needed for logistical reasons). The duration can be extended up to 4 weeks after consultation with the sponsor for subjects who achieved a response (CR, CRh, CRi, or MLFS) with no detectable blasts in bone marrow at the end of infusion. Weekly hematology assessments should be performed to confirm recovery of peripheral blood counts. Once peripheral blood counts have returned to baseline levels, the next treatment cycle can be initiated.

In subjects who achieved a response with no detectable blasts in bone marrow at end of infusion, the infusion-free interval may also be extended up to a maximum of 6 weeks in case of insufficient recovery of peripheral blood counts (neutrophils < 500/ μ L, platelets < 20 000/ μ L without transfusion) and after consultation with the sponsor. In case the infusion-free interval is extended to 4-6 weeks, a bone marrow assessment is recommended 4 weeks after the end of the infusion cycle. In case this assessment shows detectable leukemic infiltration of the bone marrow, treatment should be resumed immediately even if peripheral blood counts have not yet recovered at this time point.

6.1.1.1.2 Overdose

A dose of up to 10% higher than the intended AMG 330 dose (per day) may not require specific intervention. In case of overdose or medication error, the infusion should be immediately stopped. Routine supportive and symptomatic care according to standard medical practice is recommended. Once the subject is stabilized and no clinically relevant safety findings due to AMG 330 are observed, resumption of AMG 330 at a correct dose can be considered after consultation with the Amgen medical monitor.

For AMG 330, a dose of greater than 10% higher than the intended dose will be considered clinically important and classified as a serious adverse event under the criterion of “other medically important serious event” per [Section 11.4](#). If the overdose results in additional adverse event/s, the subject should be followed carefully until all signs of toxicity are resolved and the adverse event/s should be recorded/reported per [Section 11.4](#) of the protocol.

6.1.1.2 AMG 330 Inpatient Dosing

Subjects are required to be monitored in a hospital for a minimum of 72 hours following initiation of therapy and for a minimum of 72 hours after each dose level increase. Close monitoring is indicated because of the potential adverse events associated with T cell redistribution and potential cytokine release effects triggered by the administration of

AMG 330. Nurses/physicians familiar with such conditions should be available for immediate intervention in case of complications.

Also, if AMG 330 is interrupted for longer than 4 hours, re-start of the infusion should be performed in the hospital, under the supervision of the investigator or designee. The subject should be observed overnight for possible side effects after the re-start, either in the hospital or in the outpatient setting as applicable. Administration of dexamethasone premedication will occur as described in [Section 6.7](#).

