6.1.1.3 AMG 330 Outpatient Dosing

Apart from the situations where inpatient dosing is required per [Section 6.1.1.1.2](#), and if deemed stable by the investigator, a subject may continue AMG 330 clV infusion as an outpatient. Subjects will receive a patient card indicating that the subject is participating in a clinical study. The patient card will also provide site contact details to be used in case of questions on the study or an emergency. In the outpatient setting, the subject will either return to the study site for infusion bag changes or the subject will be visited by a well-trained home health care service provider at specific intervals to change the infusion bag, measure vital signs, monitor and document adverse events and/or serious adverse events, and document any issues with the clV infusion or infusion pump. The subject and home health care service provider will be trained and will receive written instructions for storage of the IV bags, if applicable. The home health care service provider will complete the study delegation log and will be authorized by the investigator before any study-related tasks are started.

Refer to the home health care manual for detailed information on the storage, handling, and administration of AMG 330, mandatory procedures, and data collection requirements.

Following each visit or telephone contact by the home health care service provider, the information collected will be documented on the Home Health Care Services visit worksheet and forwarded to the investigator. Any unexpected or unusual events as well as any deviations will be communicated promptly to the investigator. If any adverse event occurs in the outpatient setting, the home health care service provider should directly contact the site for further management. The home health care service professionals provide 24 hour emergency on-call service for any pump related issues. In the event of an interruption of the AMG 330 clV infusion of > 4 hours, restart of the infusion should be performed in the clinic/hospital under the supervision of the

investigator or designee and the subject should be hospitalized for a minimum of 48 hours (see [Section 6.2.2.1](#)).

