6.2.2 Dosage Adjustments, Delays, Rules for Withholding or Restarting, Permanent Discontinuation

6.2.2.1 Amgen Investigational Product: AMG 330

Subjects will be monitored continuously for adverse events while on study therapy.

Subjects will be instructed to notify their physician immediately for any and all adverse events. The criteria presented in this section for dose modifications and delays for AMG 330 are meant as general guidelines.

Criteria for Dose Delay or Dose Reduction

Subjects will receive continuous AMG 330 therapy as long as they have not had disease progression or an adverse event requiring dose modification, as described below.

Subjects who experience a grade 4 non-hematologic adverse event will not receive additional protocol-related therapy and will be removed from study unless discussed and agreed upon by the Sponsor and investigators that it is in the best interest of the subject to receive additional therapy with AMG 330 (eg, if the subject has demonstrated a response to therapy).

Dose modifications, interruptions, or delays may occur in the setting of lower grade adverse events based on the clinical judgement of the investigator, and in consultation

with the sponsor. Dose reductions should be to the previous lower dose level, or to a dose level in between the previous dose level and the current dose level, after discussion between the investigator and the sponsor.

No more than 2 dose level reductions of AMG 330 will be allowed per subject. If a third dose reduction is required, the subject must discontinue AMG 330 (and pembrolizumab, if receiving combination therapy based on response to therapy). Dose re-escalation after a dose reduction may occur in limited circumstances (such as a change in attribution of adverse event, or if re-escalation is in the best interest of the subject) after discussion and agreement between the sponsor and the investigator.

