If a DLT occurs in a subject with clinical benefit from treatment, a restart at a lower dose can be considered if the toxicity has resolved to grade ≤ 1 and after consultation with the sponsor. If AMG 330 is discontinued, pembrolizumab may be continued as a monotherapy until disease progression for a maximum of 35 cycles (approximately 2 years) after discussion and agreement between the sponsor and the investigator. If pembrolizumab is discontinued, AMG 330 may be continued as a monotherapy.

Dose delay: treatment should be interrupted until the adverse event is resolved to grade ≤ 1 , and can then be resumed at the same dose unless the interruption lasted for more than 24 hours, please see below. (Note: if the event needs > 21 days to resolve, treatment has to be permanently discontinued, see also below).

Infusion Interruption

Significant events requiring a change in treatment will be managed by immediate infusion interruption:

- The subject experiences a DLT as defined in [Section 6.2.1](#)
- The subject experiences a clinically relevant grade 4 adverse event related to investigational product (see above) but does not meet the DLT criteria
- The subject meets criteria for discontinuation of investigational product as described in [Section 6.2.2](#)
- The subject experiences disease related adverse events and AMG 330 interruption is required for medical interventions
- Technical problem with the infusion pump
- The investigational product is incorrectly prepared or administered (eg, overdose)

Restarting the Infusion

Treatment may resume if the interruption is ≤ 21 days and if:

- The interruption occurred due to other reasons than toxicity (disease-related events, technical or logistic reasons; eg, diagnostic measurements). The infusion can be restarted at the same dose and without additional measures.
- The toxicity has resolved to CTCAE v5 grade ≤ 1 (in case of dose reduction, infusion may be re-started without prior resolution of the toxicity to CTCAE v5 grade ≤ 1 if the adverse event is not clinically relevant and upon discussion and agreement between the investigator and the sponsor)

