Please also refer to specific guidance on restart after CRS in [Section 6.8](#). Restarting the infusion after a treatment interruption requires care. The re-start should be performed in the hospital, under supervision of the investigator or designee, if the reason for the interruption was other than a technical issue or the interruption exceeded 4 hours independent of reason. Assessments should be performed after infusion re-start depending on the length of the interruption. The subject should be hospitalized for at least 48 hours after re-start of the infusion.

In case of an AMG 330 infusion interruption of > 24 hours, regardless of the reason for interruption, re-start of the infusion (repeat cycle) should be performed using step doses, which will be defined upon consultation with the sponsor. Only 2 repeat cycles may be performed in cycle 1. For cycle 2 and beyond, additional repeat cycles can be permitted upon discussion and agreement between the investigator and sponsor.

Step doses will be performed within 1 – 2 weeks (\pm 1 day) to return to the interrupted AMG 330 dose level, and the number and duration of repeat step doses will depend on the level of interrupted AMG 330 dose. During this 1-2 weeks, [Table 1-7 Schedule of Activities](#) should be followed (eg, for AMG 330 doses interrupted at [REDACTED] μ g/day and below, 2 step doses can be used: [REDACTED] μ g/day for 3 days followed by [REDACTED] μ g/day for 4 days; for doses interrupted above [REDACTED] μ g/day, 3 step doses can be used: [REDACTED] μ g/day for 1 day followed by [REDACTED] μ g/day for 3 days followed by [REDACTED] μ g/day for 3 days). In case of AMG 330 infusion interruption for < 24 hours, regardless of the reason for interruption, restart of infusion should be performed at the same dose level as the last dose level. Administration of pembrolizumab will remain on the Q3W schedule.

After 2 unsuccessful restarts, the subject may remain on the study and continue AMG 330 treatment with a previously tested target dose that has been well tolerated. The dose of pembrolizumab will remain unchanged.

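### After an AMG 330 interruption of more than 4 hours, Protocol 6.1.1.2 accepts overnight and possibly outpatient observation, while 6.1.1.3 and 6.2.2.1 call for at least 48 hours in hospital

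*Protocol*

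**What the plan says.** Protocol 6.1.1.2 (AMG 330 Inpatient Dosing) asks for a supervised hospital re-start after an interruption of more than 4 hours, and continues: "The subject should be observed overnight for possible side effects after the re-start, either in the hospital or in the outpatient setting as applicable".

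Protocol 6.1.1.3 (AMG 330 Outpatient Dosing) uses the same threshold of more than 4 hours, but says "the subject should be hospitalized for a minimum of 48 hours" and refers to 6.2.2.1.

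Protocol 6.2.2.1, under Restarting the Infusion, asks for an in-hospital re-start when the cause was not technical or when "the interruption exceeded 4 hours independent of reason". It then adds: "The subject should be hospitalized for at least 48 hours after re-start of the infusion".

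The same subsection also fixes the dose at re-start. Under 24 hours, "restart of infusion should be performed at the same dose level as the last dose level". Over 24 hours, "regardless of the reason for interruption, re-start of the infusion (repeat cycle) should be performed using step doses". Where step doses are used, it asks for hospitalization from re-start until 72 hours after the dose step, and the footnote on hospitalization in Table 1-7 gives the same 72-hour minimum.

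A little earlier, the list of conditions for resuming treatment covers interruptions of up to 21 days for reasons other than toxicity. There it says: "The infusion can be restarted at the same dose and without additional measures".

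**The concern.** Three sections address one event and do not agree on what follows it. An investigator who consults only the inpatient dosing section may send the subject home after the re-start. One who consults either of the other two sections will keep the subject in hospital for two days.

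The issue is monitoring for cytokine release syndrome (CRS). Section 2.3 lists CRS as an identified risk, with signs and symptoms in 67% of subjects in the first-in-human study, and notes that checkpoint inhibition may make it more frequent or more severe. Section 6.1.1.2 itself gives possible cytokine release as a reason for close monitoring. After a pause of more than 4 and less than 24 hours the infusion resumes at the previous dose without stepping up, so observation after the re-start is one of the main safeguards left. That is where the guidance diverges.

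**Working it through.** No arithmetic supports or refutes this point. The check is a comparison of the texts.

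| Place in Protocol | Trigger | After re-start |
|---|---|---|
| 6.1.1.2 | interruption > 4 h | overnight observation, in hospital or as an outpatient |
| 6.1.1.3 | interruption > 4 h | in hospital, at least 48 h; refers to 6.2.2.1 |
| 6.2.2.1, Restarting the Infusion | > 4 h for any reason (hospital re-start) | in hospital, at least 48 h |
| 6.2.2.1 and Table 1-7 | step doses, used after > 24 h | in hospital until 72 h after the dose step |

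1. *Same trigger?* Yes. The first three rows all apply once an interruption passes 4 hours.

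2. *Can all be met together?* Only in one direction. A 48-hour stay includes a night, so it satisfies 6.1.1.2 as well. Outpatient observation under 6.1.1.2 fails 6.1.1.3 and 6.2.2.1. So does a single night in hospital.

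3. *Does care setting separate them?* No. Although 6.1.1.2 is the inpatient section, it is the one that offers outpatient observation. The 48-hour sentence in 6.2.2.1 is not limited by setting. A split by heading would also give the odd result that a subject interrupted at home gets 48 hours in hospital, while one interrupted in hospital may be observed as an outpatient.

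4. *Do cross-references settle it?* Only in part. 6.1.1.3 points to 6.2.2.1, but the re-start text in 6.1.1.2 does not.

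5. *Which interruptions are mainly affected?* Those between 4 and 24 hours, a band 24 − 4 = 20 hours wide, where the re-start is at the same dose. Beyond 24 hours, step doses bring in the 72-hour rule, and 6.1.1.2 itself asks for 72 hours in hospital after each dose increase.

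6. *The sentence on additional measures.* Taken alone, it would let a subject who had been off drug for days for a logistic reason resume at the full dose. The paragraphs after it override that reading above 4 hours (hospital re-start and stay) and above 24 hours (step doses). Section 6.8 repeats the step-dose rule for more than 24 hours, whatever the reason.

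**The case against.** The best defence is that the protocol already shows which rule governs. Two sections state 48 hours and one of them refers to the other. The outpatient wording in 6.1.1.2 is qualified as applying only where applicable, and a site that follows the stricter rule complies with everything. The language is advisory throughout, and 6.2.2.1 opens its AMG 330 text with: "The criteria presented in this section for dose modifications and delays for AMG 330 are meant as general guidelines". The affected re-starts are at an unchanged dose and begin in hospital under supervision. Section 6.8 places the raised CRS risk in the first days after the initial infusion, and 2.3 describes AMG 330 toxicity as appearing shortly after dose increases.

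Much of this stands as a limit on severity. It does not reconcile the texts. The qualifier in 6.1.1.2 does not say when outpatient observation is ruled out, and the general-guidelines statement covers its own section only, not 6.1.1.2 or 6.1.1.3.

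A reader might also count the sentence on additional measures as a third competing observation rule. The documents do not support that. It is a permission within a list of conditions for resuming, and the text that follows directly qualifies it. It is loosely worded, no more.

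Nor does the conflict shown here justify new restrictions on pauses of 4 hours or less. The resuming list expressly allows for brief logistic or diagnostic interruptions, and 8.2.7 itself directs a pause if a PK sample must be drawn through the central line. Section 6.1.1.3 asks for no hospital stay after such pauses.

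**Conclusion.** The inconsistency is real and concerns subject safety. For interruptions of more than 4 hours, one sentence in 6.1.1.2 permits less monitoring than 6.1.1.3 and 6.2.2.1 call for: a night, possibly with no inpatient stay after the re-start itself, against at least 48 hours in hospital. The practical weight falls on same-dose re-starts after more than 4 and less than 24 hours. The point should be corrected, and the correction is small.

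Three stronger readings should be set aside. A reader might infer a breach of a firm requirement, but every sentence involved says *should*. A reader might take the 67% CRS figure as the risk at re-start, but it covers all treated subjects and is not specific to re-starts. A reader might infer an effect on the dose-limiting toxicity (DLT) results, but the CRS criteria in 6.2.1 turn on grade and time to resolution, not on where the subject is observed. Nothing in the documents links the conflict to an endpoint, the sample size or the stopping rule.

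The conclusion assumes that 48 hours is the intended rule, because it appears twice with a cross-reference. The documents give no frequency of such interruptions and no CRS rate after re-start, and they do not define overnight. No size of harm is claimed.

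**What to change.** 1. In 6.1.1.2, replace the overnight sentence with wording such as: *After such a re-start the subject should stay in hospital for no less than 48 hours, or until 72 hours after the dose step when step doses are used; see Section 6.2.2.1.*

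2. In 6.2.2.1, keep the sentence on restarting without additional measures and add directly after it: *For interruptions of more than 4 hours, the rules below on hospital re-start and a 48-hour stay apply; for interruptions of more than 24 hours, step doses also apply, whatever the reason.*

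The second edit leaves the handling of interruptions of 4 hours or less as it is, including short logistic, diagnostic or PK-sampling pauses.

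The cost is two sentences of protocol wording. The downside is a longer minimum stay than 6.1.1.2, or the permission in 6.2.2.1 read alone, now allows. For interruptions over 4 hours, 6.1.1.3 and the re-start text of 6.2.2.1 already call for that stay.
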